13.1.1 Hypothesis Regarding Primary Endpoint

The following hypothesis will be tested to compare the Prismaflex M150 Set extracorporeal circuit life between Prismocitrate 18 and Control group.

Null hypothesis H_0 : $\Lambda_P = \Lambda_C$

Alternative hypothesis $H_A: \Lambda_P \neq \Lambda_C$

where Λ_P relates to the cumulative hazard function for the Prismocitrate 18 group and Λ_C relates to the cumulative hazard function for the Control group.

To test the null hypothesis, the following test statistic for the clustered log rank test will be calculated:

$$CLR = \sum_{g=1}^{2} \sum_{k=1}^{K_g} LR_{gk}$$

where g represents the treatment group (g = 1 for Prismocitrate 18 and g = 2 for Control) and LR_{gk} is a partition of the log rank statistic for group g and cluster k. The number of clusters K_g can differ between treatment groups g.

The total variance can be estimated from the within cluster mean squared error MSE_{gk} . Since the clusters and treatment groups are independent the MSE_{gk} can be summed across clusters to find the total variance for CLR:

$$\operatorname{var}(CLR) = \sum_{g=1}^{2} \sum_{k=1}^{K_g} MSE_{gk}$$

$$MSE_{gk} = E(LR_{gk})^2$$

The log rank statistic for group g and cluster k can be derived as follows:

$$LR_{gk} = n \sum_{i=1}^{n_{gk}} \frac{\delta_{gki} W(t_{gki})}{Y_g(t_{gki})} - \sum_{g'=1}^{2} \sum_{k'=1}^{K_{g'}} \sum_{i'=1}^{n_{g'k'}} \frac{\delta_{g'k'i'} Y_{gk}(t_{g'k'i'}) W(t_{g'k'i'})}{Y_g(t_{g'k'i'}) Y(t_{g'k'i'})}$$

where W is a weight function specific to the log rank test:

$$W(t_{gki}) = \frac{Y_1(t_{gki})Y_2(t_{gki})}{Y(t_{gki})}$$

and n is the total number of observations,

ngk is the number of observations in cluster k within treatment group g,

 δ_{gki} is the number of failures in group g and cluster k,

 $Y_g(t_{gki})$ is the number at risk in group g at the observed time (either censoring or failure) for observation i in group g and cluster k,

 $Y_{gk}(t_{g'k'i'})$ is the number at risk in group g and cluster k at some time t where g', k' and i' can vary independent of g, k and i to any value within the range of g, k and i.

It has been proven that CLR converges to a normal distribution under H₀. Thus, the Wald test resolves to a standard normal distribution:

$$Z = \frac{CLR}{\sqrt{\text{var}(CLR)}} \sim N(0,1)$$

According to the standard procedure for any statistical test we will reject H_0 when Z exceeds the critical value for a given level of Type I error.

At Interim Analysis:

The p-value p_1 will be based on the test statistic Z above and on the subset of subjects completing treatment at the time point of the interim analysis (50% of subjects).

If $p_1 < 0.0087$, reject H_0 and claim difference in cumulative hazard function between treatment groups

If $p_1 \ge 0.0087$, do not reject H_0 and continue enrollment of subjects

At Final Analysis (End of Study):

The p-value p_2 will be based on the test statistic Z above and on the subset of subjects enrolled after the interim analysis (50% of subjects).

If $p_1p_2 < 0.0087$, reject H_0 and claim difference in cumulative hazard function between treatment groups

If $p_1p_2 \ge 0.0087$, do not reject H_0

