5.2 Sample Size

A sample size of 80 patients in each treatment group will provide > 90% power for assessing the equality of the extracorporeal circuit life between treatment groups using a two-sided clustered log-rank test with an overall alpha level of 0.050. This is based on the following assumptions: median circuit lives of and in the Prismocitrate 18 and Control group, filters per patient (during the Evaluation period of 120 hours) in the Prismocitrate 18 and Control group, of subjects discontinuing therapy for reasons other than due to clotting of the circuit (i.e., common exponential dropout rate of), a single interim analysis when 50% of patients have

completed treatment, and combination of results from the two study stages (prior to vs after interim analysis) using Fisher's combination test⁹.

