Filters used after a patient crossed-over treatment to the other study treatment group (switch from Prismocitrate 18 to Control, or switch from Control to Prismocitrate 18) will be analyzed under the original, randomized treatment assignment following the intent-to-treat principle. Each filter used during the 120 hours observation period or until treatment is finished will be included in the statistical analysis (several filters per patient). The potential dependence between extracorporeal circuit lives within the same patient will be accounted for using a clustered log rank test.

Separate estimates per treatment group will be provided for the primary endpoint based on Kaplan-Meier methodology. These estimates of the survival functions will be graphically displayed and tabulated as cumulative distribution functions. Characteristic values of these functions such as Q1, median survival time and Q3, will be provided and differences between estimated survival functions will be assessed using a clustered log rank test ¹¹.

This clustered log rank test provides advantages over readily available methods to analyze clustered survival data, such as the PHREG procedure using the covariance sandwich estimator option and the NLMIXED procedure for accelerated failure time frailty models, both available in SAS, due to its complete non-parametric nature. No

assumptions about the distribution of the data or the structure of the covariance matrix have to be made. Details on the underlying clustered log rank test are provided in Section 13.1.1 Hypothesis Regarding Primary Endpoint.

Analyses of the primary endpoint will be carried out on the FA based on the randomized treatment groups (intent-to-treat principle) as well as the PP.

An interim analysis will be carried out after 50% of subjects completed treatment. Please refer to Section 13.5 Interim Analysis for further details regarding the interim analysis.

The study will be stopped early due to overwhelming efficacy when a p value of < 0.0087 is observed using the clustered log-rank test at the interim analysis (critical value based on Bauer & Koehne⁹ procedure with no early stopping for futility). If $p \ge 0.0087$ and the study continues enrollment into a second stage, Fisher's combination test will be performed at the end of the study using a critical value of 0.0087 (c_α) which guarantees that the overall Type I error is controlled and preserved at a maximum of 0.05:

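### As transcribed, SAP 13.1.1 adds the two arms' log-rank parts where the log-rank numerator is their difference, so the Z it defines does not have the N(0,1) distribution it states

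*SAP*

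**What the plan says.** SAP 13.1 names the clustered log-rank test as the primary analysis and points to one place for its definition: "Details on the underlying clustered log rank test are provided in Section 13.1.1 Hypothesis Regarding Primary Endpoint". Protocol 8.5.1 names the same test and gives no formula.

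SAP 13.1.1 introduces the statistic with "To test the null hypothesis, the following test statistic for the clustered log rank test will be calculated". As transcribed, the displayed lines are:

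- CLR = Σ_g Σ_k LR_gk, over g = 1 (Prismocitrate 18) and g = 2 (Control), with no sign attached to g.
- LR_gk = n Σ_i δ_gki W/Y_g − Σ δ_g'k'i' Y_gk W/(Y_g Y), in the same form for both arms.
- W = Y1·Y2/Y, symmetric in the arms.
- var(CLR) = the sum of the squared LR_gk over all clusters in both arms.

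The factor is explained by "and n is the total number of observations". The section then says "It has been proven that CLR converges to a normal distribution under" H0, and "Thus, the Wald test resolves to a standard normal distribution". It rejects "when Z exceeds the critical value for a given level of Type I error". For the interim analysis, p1 "will be based on the test statistic Z above and on the subset of subjects completing treatment"; p2 is based on the same Z in the patients enrolled afterwards. Both feed the 0.0087 rule.

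**The concern.** A log-rank statistic contrasts two arms. If the contributions are defined identically in each arm, a contrast needs a minus sign somewhere, and the transcribed section has none: not in CLR, not in LR_gk, not in W. The variance line is right for a difference of arm totals but does not match their sum. The section therefore contradicts itself: the CLR it prints cannot have the null distribution it claims.

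What is at stake is the pre-specified definition of the primary p-values. The interim decision, the final decision through p1·p2, and the per-protocol and censoring analyses of SAP 13.2 all rest on this Z. Anyone coding or validating from 13.1.1 would not obtain the log-rank result.

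**Working it through.** **The plan's own boundary.** c_α = exp[−½ χ²_4(0.95)] = 0.008705, so the stated 0.0087 reproduces. The boundary is not in question.

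**Algebra (no redacted input needed).** At each event time let d1 and d2 be the events by arm, d = d1 + d2, and u = d1 − d·Y1/Y (observed minus expected in arm 1). Take n as a common factor, or drop it, and sum LR_gk over the clusters of arm g. Each event time contributes W(d_g/Y_g − d/Y).

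- Arm 1: (Y1Y2/Y)(d1/Y1 − d/Y) = (Y2/Y)u.
- Arm 2: (Y1Y2/Y)(d2/Y2 − d/Y) = (Y1/Y)(d2 − d·Y2/Y) = −(Y1/Y)u.
- Difference: u(Y2 + Y1)/Y = u, the log-rank numerator.
- Sum: u(Y2 − Y1)/Y, close to zero while the arms have similar numbers at risk.

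If instead n multiplies only the first term, the sum becomes Σ W[n(d1/Y1 + d2/Y2) − 2d/Y]. With n the total number of circuits this is positive in practice, so Z is not centred at zero under H0.

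**Four-circuit example.** One circuit per patient, all clotted: Control at 10 and 20 h, Prismocitrate at 30 and 40 h. At 30 and 40 h no Control circuit is at risk, so the Control term is 0/0; it is set to 0 here.

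- At 10 h: Y1 = 2, Y2 = 2, Y = 4, W = 1. At 20 h: Y1 = 2, Y2 = 1, Y = 3, W = 2/3. At 30 and 40 h: W = 0.
- Each Prismocitrate circuit: −1/(2·4) − (2/3)/(2·3) = −0.125 − 0.111 = −0.236. Arm 1 total: −0.472.
- Control at 10 h: 1/2 − 0.125 = 0.375. Control at 20 h: 0.667 − 0.125 − 0.222 = 0.319. Arm 2 total: 0.694.
- Variance: 2(0.236²) + 0.375² + 0.319² = 0.354, square root 0.595.
- Sum as transcribed, n neutral: +0.222, Z = +0.37.
- Difference: −1.167, Z = −1.96. Direct check: O − E in arm 1 = 2 − (2/4 + 2/3 + 1 + 1) = 2 − 3.167 = −1.167.
- Sum with n = 4 on the first term only: −0.472 + (2 − 0.125) + (2.667 − 0.347) = 3.722; variance 9.007; Z = +1.24.

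Neither reading of the sum gives the log-rank value.

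**Simulation.** From the plan: 80 patients per arm, 120 h per patient, 72 h cap per circuit, several circuits per patient, half the patients in each stage. Assumed, because the medians and filters per patient are redacted: exponential circuit lives with gamma frailty, in two sets of inputs.

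- Set 1: null median 20 h, frailty variance 0.3 (also 0.01 and 1.0), non-clotting removal median 72 h or none.
- Set 2: null medians 15, 25 and 40 h, frailty variance 0 or 0.5, hazards of 0.01/h for other circuit changes and 0.003/h for discontinuation, 80 and 40 patients per arm.

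| Statistic under H0 | Set 1 (80 per arm) | Set 2 (80 and 40 per arm) |
|---|---|---|
| Sum, n neutral | SD of Z 0.026 to 0.037; rejects 0% | SD of Z 0.04 to 0.07; rejects 0% |
| Sum, n on first term only | mean Z 8.5 to 11.3; rejects 100% | mean Z 6.0 to 10.9; rejects 100% |
| Difference, n neutral | SD of Z 0.98; rejects 4.5% | SD of Z 0.99 to 1.03; rejects 4.5% to 5.9% |
| Difference, n on first term only | SD of Z 0.54; rejects 0% | SD of Z 0.40 to 0.70; rejects at most 0.5% |

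With a true effect (set 1, Control vs Prismocitrate medians, n neutral), the difference rejects in 91% of trials at 20 vs 30 h and the sum in 0%. The sum still rejects 0% at 20 vs 40 h and reaches 25.6% only at 6 vs 72 h. Correcting the sign but leaving n on the first term gives 48% at 20 vs 30 h.

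**The case against.** The strongest reply is that this may be damage from PDF reading. The equations were extracted by a program, and n on one term only is just what a lost bracket would look like. That stands for n, and it is why the original page must be checked first. It is weaker for the sum: the CLR line reads as complete, and no placement of n rescues it. A lost minus sign remains possible but is not shown.

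The second reply is that the intent is plain. Both documents name the test, the SAP's reference list cites a published SAS macro with a link to its code, and 13.1.1 itself requires a standard normal Z. A program with a null SD near zero, or a null mean near 10, should fail basic validation. This stands as to intent, and it blocks a stronger inference: a reader might conclude that the trial's primary p-values are wrong, or that the trial ran with 0% power or 100% type I error. The documents do not show the code and do not support that. Citing a macro does not, however, correct the one formula the SAP commits to.

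A reader might also infer from the missing absolute value that the test is one-sided. It is not. The alternative hypothesis is a plain inequality, SAP 5.2 specifies a "two-sided clustered log-rank test with an overall alpha level of 0.050", and SAP 8.1 sets a two-sided level. That is wording only.

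**Conclusion.** The concern holds for the formula as transcribed. The sum over arms is not the log-rank numerator, and Z is not N(0,1) under either reading of n. This follows from algebra and depends on no assumed value. The sizes do depend on assumptions: a null SD of roughly 0.03 to 0.07 with n neutral, or 100% null rejection with n on the first term only, under assumed medians, frailty and removal rates. The two readings have opposite consequences, so neither figure predicts what happened in the trial. The named test, the two-sided level and the 0.0087 boundary are unaffected, and no error in the executed analysis is shown. The defect is confined to the written definition of the primary statistic, conditional on the original page reading as transcribed.

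**What to change.** 1. Check the sign in CLR and the position of n in LR_gk on the original SAP page.
2. If they are as transcribed, write CLR = Σ_k LR_1k − Σ_k LR_2k and keep the variance line. Apply n to both terms or drop it; it then cancels in Z. Correcting the sign alone is not enough if n really sits on one term.
3. Confirm that the program reproduces the corrected formula on a small test case. The four-circuit example (CLR −1.167, variance 0.354, Z −1.96) serves if the SAP states that terms with Y_g = 0 are set to 0. Alternatively, censor the two Prismocitrate circuits at 30 and 40 h and sum over event times only. Both arms are then at risk at each event (10 and 20 h). The results are the same, because the later times contributed nothing: O − E = 0 − (2/4 + 2/3) = −1.167.
4. As a wording clean-up, state rejection on |Z|, with p = 2(1 − Φ(|Z|)).

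The cost is one equation, one sentence and one program check. The boundary, sample size, data collection and named test do not change.

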8.8 Interim Analysis

A single interim analysis will be conducted when 50% of patients have completed treatment. The purpose of the interim analysis is to evaluate the primary efficacy endpoint for overwhelming efficacy, or the need to adjust the sample size. If the primary analysis yields a statistically significant test result (p < 0.0087, critical value for clustered log rank test based on Bauer & Kohne procedure with no early stopping for futility) on the FA Set, and if further no safety concern or other considerations require continuation of enrollment, the study will be stopped for overwhelming efficacy. Otherwise enrollment of subjects will continue and the whole statistical analysis as described in this document will be carried out at the end of the study using Fisher's combination test.[18] This approach guarantees that an overall type 1 error of 0.05 is preserved.

Sample size re-estimation at the interim analysis will be based on Fisher's criterion (Fisher's combination test). Simulation studies will be run utilizing the p value observed at the interim analysis (p1) and the initial assumptions for median survival times in the two treatment groups (in the Prismocitrate 18 and Control group). Re-assessment of the sample size will target a conditional power of 90% for rejecting the null hypothesis given the observed p value of the interim analysis.

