8.1 General/Types of Analyses

Unless otherwise specified, treatment effects will be evaluated on the basis of a 2-sided significance level of 0.050 (when rounded to 3 decimal places). All analyses will be performed using Statistical Analysis Software (SAS®), SAS/GRAPH® and SAS/STAT® software, Version 9.2 of SAS for Windows, Copyright© 2018 SAS Institute Inc., on a Microsoft Windows Server. SAS and all other SAS Institute Inc. product or service names are registered trademarks or trademarks of SAS Institute Inc., Cary, NC, USA¹0.

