$$p_1 p_2 \le c_\alpha = \exp\left[-\frac{1}{2}\chi_4^2(1-\alpha)\right]$$

where p_1 is the observed error probability for the test in the subsample of subjects investigated before the interim analysis,

and p_2 is the observed error probability for the test in the subsample of subjects enrolled after the interim analysis,

and $\chi_4^2(1-\alpha)$ is the $(1-\alpha)$ -quantile of the central χ^2 distribution with 4 degrees of freedom.

If $p_1 \le c_\alpha$ one could already stop at the interim analysis with the rejection of the null hypothesis since $p_2 \le 1$ holds per definition.

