13.5 Interim Analysis

The analysis described under 13.1 Primary Analysis will be carried out after 50% of patients have completed treatment. The purpose of the interim analysis is to evaluate the primary efficacy endpoint for overwhelming efficacy, or the need to adjust the sample size. If the primary analysis yields a statistically significant test result (p < 0.0087, critical value for clustered log rank test based on Bauer & Koehne procedure with no early stopping for futility) on the FA, and if further no safety concern or other considerations require continuation of enrollment, the study will be stopped for overwhelming efficacy. Otherwise enrollment of subjects will continue and the whole statistical analysis as described in this document will be carried out at the end of the study using Fisher's combination test (please see Section 13.1 Primary Analysis for details). This approach guarantees that an overall Type I error of 0.05 is preserved.

In order to re-assess the sample size for the subset of subjects recruited after the interim analysis, simulation studies will be run utilizing the p-value observed at the interim analysis (p₁). The re-assessment of the sample size will be carried out using the original assumptions for median circuit life times in the two treatment groups (in the Prismocitrate 18 and control group) and will target a conditional power of 90% for rejecting the null hypothesis given the observed results of the interim analysis.

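### Fisher's product uses unsigned two-sided p-values, so the final test can reject H0 when the two stages point in opposite directions

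*SAP*

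**What the plan says.** SAP 5.2 and Protocol 8.2 size the trial "using a two-sided clustered log-rank test with an overall alpha level of 0.050". SAP 8.1 sets the general rule that "treatment effects will be evaluated on the basis of a 2-sided significance level of 0.050". SAP 13.1.1 gives a not-equal alternative for the cumulative hazards and rejects "when Z exceeds the critical value for a given level of Type I error", without saying which arm a positive Z favours.

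SAP 13.1 defines p1 as "the observed error probability for the test in the subsample of subjects investigated before the interim analysis", and p2 likewise for subjects enrolled afterwards. Three rules use these values:

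- **Final analysis (SAP 13.1.1).** If p1*p2 < 0.0087, reject and "claim difference in cumulative hazard function between treatment groups".
- **Interim stop (SAP 13.1, Protocol 8.5.1).** "The study will be stopped early due to overwhelming efficacy when a p value of < 0.0087 is observed". Protocol 8.8 and SAP 13.5 add only that no safety or other reason calls for further enrolment.
- **Re-estimation.** Protocol 8.8 targets a "conditional power of 90% for rejecting the null hypothesis given the observed p value of the interim analysis". In SAP 13.5, "simulation studies will be run utilizing the p-value observed at the interim analysis", with the original median circuit lives; there the conditional power refers to the interim results, a wider term than the p-value.

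The primary objective (Protocol 2.1, SAP 4.1) is directional: Prismocitrate 18 should prolong circuit life.

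**The concern.** An ordinary two-sided test takes its direction from a single estimate. Here two unsigned p-values are multiplied, so two moderately small p-values from contradictory stages can reject together. The resulting claim of a difference then has no consistent direction, although the trial asks whether circuits last longer.

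The re-estimation inherits the problem. A given p1 produces the same stage 2 whichever arm is ahead, so evidence against Prismocitrate 18 at the interim lowers the hurdle for stage 2 exactly as evidence in its favour would. The delivered-dose test (Protocol 8.5.2, SAP 13.3) opens on any significant primary result, so it has the same gap.

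**Working it through.** **Inputs from the documents.** Two-sided overall alpha 0.05; critical value 0.0087; interim at 50% of 160 patients, hence 80 per stage; 90% conditional power.

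**Assumptions.** Two independent, equal-information, approximately normal stages. The medians, filters per patient and dropout rate are redacted. The drift (expected pooled Z at 160 patients) is therefore taken from 3.53, the smallest giving 90% power under the written rule, to 4.5.

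**1. The plan's own figure.** c = exp[-0.5 × chi-square(4 df, 0.95)] = 0.008705, which rounds to 0.0087. Overall error is c(1 − ln c) = 0.0087 × (1 − ln 0.0087) = 0.04998. Both stated values reproduce.

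**2. Composition of that 5% under H0.** Interim rejection is 0.0087, half of it favouring Control. Rejection at the end is 0.0500 − 0.0087 = 0.0413. The signs of the two stages are independent of p1 and p2, so half of this, 0.0206, comes from stages pointing opposite ways. Simulation gives the same figure, and about 97% of these cases have an equal-weight pooled |Z| below 1.96.

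**3. Example.** Z1 = +2.0 and Z2 = −2.0 give p1 = p2 = 0.0455. The product is 0.0021 < 0.0087, so H0 is rejected although the pooled Z is 0. With one-sided p-values the product is 0.0228 × 0.9772 = 0.022, above c = exp[-0.5 × chi-square(4 df, 0.975)] = 0.0038, so H0 is not rejected.

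**4. With a real effect** (numerical integration over Z1):

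| Drift | Power: written rule | Power: one-sided, c = 0.0038 | Power: 0.0087, every stage must favour Prismocitrate | Opposite-direction rejections: written / one-sided | Interim stop: written / one-sided |
|---|---|---|---|---|---|
| 3.53 | 90.0% | 93.0% | 89.7% | 0.34% / 0.36% | 44.8% / 43.0% |
| 4.0 | 96.0% | 97.4% | 95.8% | 0.15% / 0.16% | 58.1% / 56.3% |
| 4.5 | 98.7% | 99.3% | 98.7% | 0.06% / 0.06% | 71.2% / 69.6% |

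**5. Re-estimation, illustrated at two-sided p1 = 0.30.** Stage-2 size = 80 × [d2 / (drift/√2)]², where d2 = required Z2 + 1.282. At drift 3.53 the denominator is 3.526/√2 = 2.493.

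- Written rule, either direction: p2 < 0.0087/0.30 = 0.0290 two-sided, Z2 = 2.183, d2 = 3.465. Size is 80 × (3.465/2.493)² ≈ 155.
- Signed, Prismocitrate ahead: p2 ≤ 0.003804/0.15 = 0.0254 one-sided, d2 = 3.235. Size ≈ 135.
- Signed, Control ahead: p2 ≤ 0.003804/0.85 = 0.00448 one-sided, d2 = 3.895. Size ≈ 195.

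At drift 4.5 the sizes are about 95, 83 and 120.

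With Control ahead (Z1 = −1.036), the written rule rejects from Z2 = 2.183. Weighted by 80 and 155 patients, the pooled Z is 1.17 (p = 0.24). With 80 and 95 patients it is 0.91 (p = 0.36).

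**6. How often this arises.** An interim favouring Control has probability 0.63% to 0.07% over drifts 3.53 to 4.5, and 0.02% to 0.001% if p1 ≤ 0.30 is also required. Under H0 the figures are 50% and 15%.

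**The case against.** There is a good case that this is mainly a matter of wording.

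- **Error control.** A reader might infer that type I error is inflated. It is not. Flipping both stage signs leaves p1, p2 and the stage-2 size unchanged. If direction is read from the pooled result, a false claim for Prismocitrate 18 is therefore limited to 2.5%. The 2.06 points describe the composition of a permitted 5%, not an excess. This stands.
- **Interim stop.** A reader might infer that the trial could stop and declare efficacy when Control circuits last longer. No formal sign condition excludes it. However, the stop is for efficacy, and the objective defines that as prolonging circuit life. Protocol 9.8 also lets the data monitoring committee stop if treatment is shown not to be beneficial. On a natural reading the direction is implied, so this part largely falls away.
- **Re-estimation.** It follows from the unsigned product: for the test as written, the sizing does deliver 90% conditional power. Only Protocol 8.8 conditions on the p-value alone. SAP 13.5 does not exclude the sign, although p1 is its named simulation input. This stands, so it is a consequence and not a separate error.
- **One-tailed reading of Z.** The phrase about Z exceeding a critical value might suggest an upper-tail test. That conflicts with the stated two-sided test and the not-equal alternative, and no sign convention supports it.
- **Kaplan-Meier estimates by arm.** They show the direction to a reader but change neither the rejection rule nor the stage-2 size.

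**Conclusion.** The point holds for the final combination rule and, through p1, for the re-estimation. As written, the plan can reject H0 on contradictory stages (2.06 of 5.00 points under H0) and can size stage 2 from an unfavourable interim as if it were favourable. The interim stop needs only a clarifying phrase.

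Two further inferences are not supported. The stated power above 90% is not shown to be wrong: its inputs are redacted, and the drifts used here are assumptions. Nor is the problem frequent if the design effect is real: opposite-direction rejections are then 0.34% to 0.06%. The H0 figures need only independent, equal-information, approximately normal stages; the power and patient numbers also depend on the assumed drift. Severity is minor to moderate.

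**What to change.** Amend the SAP and protocol wording before the interim result is known.

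**Preferred.** State which arm a positive Z favours. Define p1 and p2 as one-sided for longer circuit life with Prismocitrate 18. Reject in that direction if p1 ≤ 0.0038 or p1*p2 ≤ 0.0038. Run the mirror test for Control at the same level, so that overall two-sided error stays at 5%. Reserve the efficacy stop and the delivered-dose gate for the Prismocitrate direction, and use the signed p1 in the re-estimation.

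- Gain: 3.0 to 0.6 points of power over the assumed drifts, and opposite-direction rejections under H0 fall from 2.06 to 0.67 points. They do not vanish, and they do not fall under a real effect (0.34% against 0.36% at drift 3.53).
- Cost: the interim boundary tightens to a two-sided equivalent of 2 × 0.0038 = 0.0076, which lowers the chance of stopping early by 1.6 to 1.8 points. A re-estimated stage 2 becomes larger after an interim favouring Control and smaller after one favouring Prismocitrate. The planned 160 patients do not change.

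**Minimal alternative.** Keep 0.0087 and claim efficacy only if every stage analysed favours Prismocitrate 18. This removes all opposite-direction efficacy claims at a cost of at most 0.3 points of power (90.0% to 89.7% at drift 3.53). The chance of a false efficacy claim under H0 is then 1.47%. An interim favouring Control could no longer lead to an efficacy claim, so the SAP must also say what happens to the re-estimation in that case.
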